#### 8.2.3 CHEST X-RAY

Bidirectional posterior-anterior and lateral view chest X-ray will be performed at screening ([Section 1.3](#)). If a chest X-ray was performed within 6 months of screening and no clinically significant abnormality was observed, it can be skipped at screening.

## 8.2.4 PHYSICAL EXAMINATIONS

Complete physical examinations will be performed at the time points indicated in the SoA ([Section 1.3](#)).

A complete physical examination will include assessments of general appearance; skin; head/neck; pulmonary, cardiovascular, gastrointestinal, lymphatic, and musculoskeletal system; extremities; eyes; nose; throat; and neurologic status. The indication under study, hidradenitis suppurativa, should not be reported as part of the physical examination.

A detailed examination of the skin should be performed at the time points indicated in the SoA for the efficacy assessments (eg, AN count).

Investigators should pay special attention to clinical signs related to previous serious illnesses.

## 8.2.5 VITAL SIGNS

Body temperature (°C), pulse rate (bpm), blood pressure (mmHg), and respiratory rate (breath/min) will be assessed at the time points specified in SoA ([Section 1.3](#)).

Blood pressure and pulse rate will be assessed in a seated position with a completely automated device. Manual techniques will be used only if an automated device is not available.

Assessments should be preceded by at least 5 minutes of rest for the subject in a quiet setting without distractions (eg, television, cell phones).

Vital signs including body temperature, respiratory rate, and pulse rate (after at least 5 minutes rest) should be measured once. Arterial blood pressure should be measured once, using a validated device, and recorded in the eCRF.

## 8.2.6 ELECTROCARDIOGRAMS

A single 12-lead ECG will be obtained at the time points specified in the SoA (see [Section 1.3](#)) using a validated ECG machine that automatically calculates the heart rate and measures RR, PR, QRS, QT, and QTcF intervals.

Additional information will be provided in a separate manual.

The ECG will be reviewed by the Investigator or an authorized representative who is experienced in the evaluation of ECGs and assessed for clinical significance.

The ECG individual data (including clinical significance that will be reported as AE) will be entered into the electronic data capture (EDC).

## 8.2.7 CLINICAL SAFETY LABORATORY ASSESSMENTS

See [Appendix 11](#) for the list of clinical laboratory tests to be performed and the SoA ([Section 1.3](#)) for the timing and frequency of the tests.

A central laboratory will be used to perform all laboratory tests except urine pregnancy dipstick which will be assessed by the study site staff. However, local laboratory tests will be allowed in the event that the central laboratory results will not be available immediately and the Investigator needs to make an immediate decision for any safety concerns based on laboratory results. If a local sample is required, it is important that the sample for central analysis is obtained at the same time.

The Investigator must review the laboratory report, document this review, and record any clinically relevant changes occurring during the study in the AE section of the eCRF. The laboratory reports must be filed with the source documents. Clinically significant abnormal laboratory findings are those that are not associated with the underlying disease, unless judged by the Investigator to be more severe than expected for the subject's condition.

All laboratory tests with values considered clinically significantly abnormal during the study and including the subject's last study visit (EOS) should be repeated until the values return to normal or Baseline or are no longer considered clinically significant or judged medically stabilized by the Investigator or Medical Monitor.

If such values do not return to normal/Baseline within a period of time judged reasonable by the Investigator, the etiology should be identified, and AnaptysBio notified.

All protocol-required laboratory assessments, as defined in [Appendix 11](#), must be conducted in accordance with the Laboratory Manual and the SoA.

If laboratory values from non-protocol specified laboratory assessments performed at the institution's local laboratory require a change in subject management or are considered clinically significant by the Investigator (eg, SAE or AE), then the results must be recorded in the eCRF.

### 8.3 OTHER ASSESSMENTS

#### 8.3.1 FITZPATRICK SKIN TYPE CLASSIFICATION

The Fitzpatrick skin type ([Attwa 2016](#); [Fitzpatrick 1988](#); [Wallace 2017](#); [Zalaudek 2007](#)) will be evaluated at screening as described in [Appendix 12](#). Fitzpatrick skin type may be collected after the screening if missed during this visit.

#### 8.3.2 PHOTOGRAPHY

Photography (of representative lesion[s], fistulas, and scarring) is an optional procedure for all subjects at each of the specified visits at selected site.

Additional information on photography will be described in the photography manual provided to study sites.

#### 8.3.3 PHARMACOKINETICS

Whole blood will be obtained for the determination of imsidolimab concentration in human serum. Samples will be collected according to the SoA ([Section 1.3](#)) and [Table 5](#). Whole blood

will be obtained from each subject for PK assessments during the study. Each serum sample will be divided into 2 aliquots (1 each for primary and a back-up). Samples collected for analyses of imsidolimab serum concentration also may be used to correlate exposure to safety or efficacy as well as supportive analysis for dose justification.

The actual date and time (24-hour clock) of the blood sample collection will be recorded in the subject's eCRF. The details of blood sample collection, sample tube labeling, sample preparation, storage, and shipping procedures will be described in a separate laboratory manual.

The measurement of the concentrations of imsidolimab will be performed using a validated assay method under the supervision of AnaptysBio. The analytical methods used to measure concentrations of imsidolimab will be described in a separate bioanalytical report.

Only samples within the stability window of the assay will be analyzed.

While PK samples must be collected from subjects randomized to the placebo arm to maintain the blinding of treatment assignment, PK assay results for these subjects are not needed for the safe conduct or proper interpretation of this study. These samples may not be analyzed unless needed to investigate if a dosing error has occurred. Personnel at the bioanalytical laboratory performing PK assays will be unblinded, the clinical study team members, and study site staff (with the exception of the unblinded Pharmacist) will remain blinded to treatment for the duration of the study. Data may be de-identified for quality review. Additional details on de-identification or unblinding of the PK data, if applicable, will be described in a separate plan.

Drug concentration information that may unblind the study will not be reported to study sites or blinded personnel until the study has been unblinded.

**Table 5: Pharmacokinetic and Anti-drug Antibody Collection Schedule**

Study Visit	PK Sample Time Point	ADA Sample Time Point
Day 1	Predose	Predose
Day 29	Predose	Predose
Day 57	Predose	Predose
Day 85	Predose	Predose
Day 113	Predose	Predose
Day 141	Predose	Predose
Day 169	Predose	-
Day 197	Predose	-
Day 225	Anytime	Anytime
Day 253	Anytime	-
Day 281	Anytime	Anytime

Abbreviations: ADA, anti-drug antibody; hr, hours; min, minutes; PK, pharmacokinetic

### 8.3.4 IMMUNOGENICITY ASSESSMENTS

Anti-drug antibodies to imsidolimab will be evaluated in serum samples collected from all subjects according to the SoA (Section 1.3) and Table 5. Additionally, serum samples also should also be collected at the final visit from subjects who discontinued study treatment or were

withdrawn from the study. These samples will be tested by AnaptysBio or its designee. Each serum sample will be divided into 2 aliquots (1 each for primary and a back-up).

The detection and characterization of antibodies to imsidolimab will be performed using a validated assay method by or under the supervision of AnaptysBio.

Serum samples will be tested in a multi-tiered approach. A validated screening assay for antibodies binding to imsidolimab initially will be used to assess serum samples. Samples that are determined putative positive in the screening assay then will be subjected to a confirmatory assay to demonstrate that antibodies are specific to imsidolimab. Samples that are identified as positive in the confirmatory assay will be further characterized in a validated titer assay and the titer of confirmed positive samples will be reported. Other analyses may be performed to verify the stability of antibodies to study treatment and/or to further characterize the immunogenicity of study treatment.

Samples that are confirmed positive for antibodies binding to imsidolimab may be further characterized for their ability to neutralize the activity of the study treatment using a validated neutralizing antibody assay method and the presence and/or titer of ADA may be correlated to safety and PK data.

### 8.3.5 BIOMARKER ANALYSIS

The actual date and time of the biomarker sample collection will be recorded in the subject's eCRF. The details of sample collection, sample tube labeling, sample preparation, storage, and shipping procedures will be described in a separate Laboratory Manual.

The measurement of biomarkers may be performed by an additional third party (eg, a university Investigator) designated by AnaptysBio.

#### 8.3.5.1 TAPE STRIPPING

Tape strip samples will be collected from non-lesional and lesional skin according to the SoA ([Section 1.3](#)) to measure cutaneous biomarkers including but not limited to IL-36R, Th-17 cytokines such as IL-17A, and markers of neutrophils and dendritic cell infiltration.

#### 8.3.5.2 DRAINAGE FLUID COLLECTION

Optional noninvasive collection of drainage fluid to assess biomarkers may be conducted at any visit after screening. Drainage fluid should be collected where present from areas that are draining the most.

## 9 STATISTICAL CONSIDERATIONS

### 9.1 STATISTICAL HYPOTHESES

The primary analysis for this study is to compare the mean AN count for imsidolimab with placebo during the double-blind treatment period, at a two-sided alpha = 0.10 level. Any testing being performed for secondary or exploratory endpoints will be considered exploratory in nature based on a 2-sided alpha = 0.10

$H_0: \mu_{\text{imsidolimab}} - \mu_{\text{Placebo}} = 0$  vs.  $H_A: \mu_{\text{imsidolimab}} - \mu_{\text{Placebo}} \neq 0$

### 9.2 SAMPLE SIZE DETERMINATION

Approximately 120 subjects will be randomized in a 1:1:1 ratio to receive one of the following study treatments:

1. Imsidolimab 400 mg on Day 1 followed by 200 mg on Days 29, 57, and 85
2. Imsidolimab 200 mg on Day 1, followed by 100 mg on Days 29, 57, and 85
3. Placebo on Days 1, 29, 57, and 85

For this phase 2 study, the sample size was chosen empirically. Assuming a total of 10% of subjects will discontinue prior to Week 16, there will be approximately 108 evaluable subjects (36 subjects in each arm) at the end of Week 16. The study has 80% power to detect a between-group treatment difference of 4.9 lesions in the primary endpoint of mean change from Baseline in the AN count at Week 16, using a two-sided, equal-variance two-sample t-test at the  $\alpha = 0.10$  level, with the assumption of a common standard deviation (SD) of 8.2 lesions. The assumption was based on PIONEER 1 study (Kimball 2016). Table 6 shows more information on power from a set of scenarios of variability and between-group mean differences.

**Table 6: Power Exploration for Different Scenarios of Variability and Between-Group Mean Differences**

Common standard deviation	Between-group mean difference	Power (%)	
		1-sided test	2-sided test
7.2	2	46	32
	3	68	54
	4	86	76
	5	95	90
	2	40	27
8.2	3	60	46
	4	78	66
	5	90	82
	2	36	24
	3	54	39
9.2	4	71	57
	5	84	74

Note: An equal variance two-sample t-test at alpha=0.10 is used for the power calculations.

## 9.3 POPULATIONS FOR ANALYSES

The analysis sets are defined in [Table 7](#).

**Table 7: Analysis Sets**

Analysis Set	Description
ITT Analysis Set	The ITT analysis set will include all randomized subjects. In this analysis set, treatment will be assigned based upon the treatment arm to which subjects were randomized regardless of which treatment they receive. ITT analysis set will be used for primary, secondary, and exploratory efficacy analyses.
Safety Analysis Set	The Safety Analysis Set will include all randomized subjects who receive at least 1 dose of imsidolimab or placebo. The Safety Analysis Set will be used for all safety analyses. Subjects will be analyzed as treated.
Extension Analysis Set	The Extension Analysis Set is a subset of the Safety Analysis Set who receive at least 1 dose of imsidolimab in the extension period. The Extension Analysis Set will be used for summarizing both efficacy and safety data for those subjects who entered the extension period. Subjects will be analyzed as treated.
Per Protocol Analysis Set	The per protocol analysis set will include all subjects in the ITT analysis set who do not have major protocol violations that would affect the evaluation of the primary efficacy endpoint.
PK Analysis Set	The PK analysis set will include all imsidolimab-treated subjects in the Safety Analysis Set who have at least 1 quantifiable postdose PK sample available and who do not have events or protocol deviations or events with the potential to affect PK concentrations. The PK analysis set will be used for all PK analyses.

Abbreviations: ITT, intent-to-treat; PK, pharmacokinetic

## 9.4 STATISTICAL ANALYSES

### 9.4.1 GENERAL APPROACH

The statistical analysis will be performed using SAS® Version 9.4 or higher. All details regarding the statistical analysis and the preparation of tables, listings, and figures will be described in the Statistical Analysis Plan (SAP).

The default summary statistics for continuous variables include number of contributing observations, mean, SD, median, minimum, and maximum. For PK parameters, coefficient of variation (CV) and geometric mean will also be presented, as appropriate.

For categorical variables, the number and percentage (percentage of subjects in each category relative to the total number of subjects in the relevant analysis set or relative to the total number

of subjects in the relevant analysis set with assessments available [where appropriate]) in each category will be the default summary presentation.

Unless otherwise specified, “Baseline” is defined as the last observed value of the parameter of interest prior to the first intake of study treatment (this includes unscheduled visits). For numerical variables, change from Baseline will be calculated as the difference between the value of interest and the corresponding Baseline value. In the analysis of extension study subjects using the Extension Analysis Set, for those subjects who received placebo initially, their baseline will be re-calculated based on the latest data prior to receiving imsidolimab.

Unless otherwise specified, all formal statistical tests will be 2-sided at the 10% significance level. Point estimates of treatment differences will be accompanied with 2-sided 90% confidence intervals (CIs), where applicable.

In the case of normality assumption violations, appropriate nonparametric methods may be used for analysis.

All data will be presented in by-subject listings.

#### 9.4.2 SUBJECT DISPOSITION

A tabular presentation of the subject disposition will be provided. It will include the number of subjects screened, randomized, treated, completed as well as the number of dropouts with reasons for discontinuation, and major protocol deviations or violations.

A listing will be presented to describe dates of screening, assigned treatment, screen failed with reason, completion or early withdrawal, and the reason for early discontinuation, if applicable, for each subject. A list of protocol deviations/violations will be identified and discussed with the Investigator/AnaptysBio in dry run to categorize as major or minor with decisions of exclusion from analysis sets prior to unblinding.

During the COVID-19 pandemic, protocol deviations related to COVID-19 will be documented and information on how they will be handled in the analyses will be detailed in the SAP.

#### 9.4.3 BASELINE DESCRIPTIVE STATISTICS

Subject characteristics obtained at Baseline will be summarized for all subjects taking imsidolimab or placebo.

Summaries will include descriptive statistics for continuous variables (sample size [n], mean, SD, median, minimum, and maximum) and for categorical variables (n, frequency, and percentage).

Medical history will be coded using the Medical Dictionary for Regulatory Activities (MedDRA) latest version and listed for all subjects.

#### 9.4.4 CONCOMITANT MEDICATION

All medications will be coded using the World Health Organization Drug Dictionary and Anatomical Therapeutic Chemical system. Each medication will be classified as prior medication if it is stopped prior to the first dose of study treatment, or as concomitant medication if it is ongoing at the time of the first dose or is started after the first dose of study treatment. Prior, concomitant, and rescue medications will be summarized descriptively with a by-subject listing.

To handle the issue of rescue medication use, the efficacy data on and after the use rescue medication will be set to missing in the efficacy analysis.

#### 9.4.5 ANALYSIS OF THE PRIMARY EFFICACY ENDPOINT

The primary efficacy endpoint is the change from Baseline in AN count at Week 16.

The primary estimand, comprising four components, is defined as follows:

- a) The target population consists of subjects with hidradenitis suppurativa who are eligible to be included in the clinical trial based on the inclusion/exclusion criteria in the protocol. The ITT analysis set will include all randomized subjects. For the analysis, treatment will be assigned based upon the treatment arm to which subjects are randomized regardless of which treatment they receive.
- b) The primary variable is the change from baseline in AN count of an individual subject at Week 16.
- c) To handle intercurrent events such as use of rescue medications, the hypothetical strategy for estimand will be used. Data collected following receipt of rescue medication (if any) will be considered missing in the analysis.
- d) The population-level summary measures will be the population mean differences in the primary variable between each dose of imsidolimab and placebo at Week 16.

A general linear mixed effects model for repeated measures (MMRM) analysis will be used to estimate the least squares means (LSM) and associated standard errors for the change from Baseline in AN count to Week 16. The model will include change from Baseline in AN count at Week 16 as the dependent variable, fixed effects for treatment arm, categorical time point, and the treatment by time point interaction, and the Baseline AN count and stratification factor (ie, Hurley Stage at baseline (Stage II or III)) as covariates. An unstructured covariance structure will be used. The difference between LSMs (imsidolimab – placebo) at Week 16 will be presented along with the associated 90% CI and p-value. The ITT analysis set will be used for the primary efficacy analysis.

#### 9.4.6 ANALYSIS OF THE SECONDARY EFFICACY ENDPOINTS

The ITT analysis set will be used for analysis of secondary efficacy endpoints. Following are the secondary efficacy endpoints:

- Percent change from Baseline in AN count at Week 16
- Proportion of subjects achieving HiSCR50 at Week 16

- Change from Baseline in HS Pain NRS at Week 16
- Percent change from Baseline in HS Pain NRS at Week 16

#### 9.4.6.1 CATEGORICAL ENDPOINTS

Frequency and percentages for each response Yes/No for categorical endpoints will be presented separately by visit for each treatment arm. Subjects with missing scores at a given visit will be considered to have not met the criteria of interest (ie, nonresponse). Estimates of the difference between treatments (imsidolimab – placebo) will be presented along with exact 90% CIs. Treatment arms will be compared using Cochran–Mantel–Haenszel chi-squared test, adjusted for stratification factor (Hurley Stage at baseline (Stage II or III)).

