### 9.4.7 ANALYSIS OF THE EXPLORATORY ENDPOINTS

Following are the exploratory endpoints:

- Change from Baseline in AN count at visits other than Week 16
- Percent change from Baseline in AN count at visits other than Week 16
- Proportion of subjects achieving AN50 and AN75 responses
- Percentage of subjects experiencing flare, defined as a  $\geq 25\%$  increase in AN count with an absolute increase in AN count of  $\geq 2$  relative to Baseline at each visit
- Change from Baseline in abscess count at each visit
- Change from Baseline in inflammatory nodule count at each visit
- Change from Baseline in draining fistula count at each visit
- Proportion of subjects achieving HiSCR50 at visits other than Week 16
- Proportion of subjects achieving HiSCR75 at each visit
- Proportion of subjects achieving 0 (inactive) or 1 (almost inactive) on HS-PGA at each visit
- Proportion of subjects with  $\geq 2$ -point reduction from Baseline on HS-PGA at each visit
- Change from Baseline in HS-PGA
- Change from Baseline in calculated composite of abscesses, draining fistulas, and inflammatory and non-inflammatory nodules
- Change from Baseline in HS Pain NRS at visits other than Week 16
- Percent change from Baseline in HS Pain NRS at visits other than Week 16

- Proportion of subjects achieving a  $\geq$  3-point reduction on the HS Pain NRS for subjects with Baseline HS Pain NRS of at least 3
- Proportion of subjects requiring rescue medication or treatment at each visit
- Change from Baseline in DLQI score at each visit
- Change from Baseline in IHS4 at each visit
- Change from Baseline in HiSQoL at each visit
- Change from Baseline in HS-PtGA at each visit
- Proportion of subjects in each response category for the HS-PtGA at each visit
- Proportion of subjects in each response category for the PGIC at each visit
- Proportion of subjects achieving improvement (“Much better” or “Very much better”) according to the PGIC at each visit
- Proportion of subjects achieving improvement (“A little better”, “Much better” or “Very much better”) according to the PGIC at each visit
- Proportion of subjects in each response category for the PGIB at each visit
- Change from Baseline in PGIB at each visit
- Proportion of subjects achieving “A little bothered” or “Not at all bothered” for the PGIB at each visit
- Proportion of subjects in each response category for the PGIS at each visit
- Proportion of subjects achieving “Mild” or “No activity” according to the PGIS at each visit

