- Change from Baseline in PGIS at each visit
- Proportion of subjects in each category of Hurley Stage at each visit
- Change from Baseline in Hurley Stage at Weeks 16, 32, and 40
- Proportion of subjects achieving at least a 1-stage improvement in Hurley stage
- Skin tape strip and drainage fluid biomarkers analysis including, but not limited to, IL-36 and Th-17
- Presence of ADAs to imsidolimab
- Serum concentration following imsidolimab administration and other parameters as appropriate will be determined to describe the PK profile of imsidolimab

Methods for analyzing the above categorical and continuous efficacy endpoints will mirror the methods described in [Section 9.4.6.1](#) and [9.4.6.2](#), respectively. ITT analysis set will be used for analysis of exploratory efficacy endpoints.

As further additional exploratory analyses, the primary efficacy endpoint, all secondary efficacy endpoints, and some of the exploratory endpoints will be summarized using the Extension analysis population.

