#### 6.2.4 Exploratory Efficacy Variables

The exploratory efficacy endpoints are as follows:

- **Change from Baseline in AN count at Weeks other than Week 16**
- **Percent change from Baseline in AN count at Weeks other than Week 16**
- **Proportion of subjects achieving AN50 at each visit**

The number of subjects with at least a 50% decrease from baseline in AN count will be calculated at each visit.

$$\frac{\# \text{ of subjects in treatment group with } \frac{(\text{AN count at baseline} - \text{AN count at week } x)}{(\text{AN count at baseline})} \geq 50\%}{\# \text{ of subjects in treatment group with AN count at Week } x}$$

- **Proportion of subjects achieving AN75 at each visit**

For each treatment group, the number of subjects with at least a 75% decrease from baseline in AN count will be calculated at each visit. The proportion of such subjects will be calculated for each treatment group at each visit as:

$$\frac{\# \text{ of subjects with } \frac{(\text{AN count at baseline} - \text{AN count at week } x)}{(\text{AN count at baseline})} \geq 75\%}{\# \text{ of subjects in treatment group with AN count at Week } x}$$

**Proportion of subjects experiencing flare, defined as a  $\geq 25\%$  increase in AN count with an absolute increase in AN count of  $\geq 2$  relative to Baseline at each visit**

The proportion of subjects experiencing flare will be calculated for each treatment group as follows:

$$\frac{\# \text{ of subjects in treatment group experiencing flare at Week } x}{\# \text{ of subjects in treatment group with flare assessed at Week } x}$$

- **Change from baseline in abscess count at each visit**
- **Change from baseline in inflammatory nodule count at each visit**
- **Change from baseline in draining fistula count at each visit**
- **Percent change from baseline in draining fistula count at each visit (for subjects who had non-zero draining fistula counts at baseline)**

- **Change from baseline in calculated composite of abscess, inflammatory nodule, and draining fistula total count at each visit**
- **Percent change from baseline in calculated composite of abscess, inflammatory nodule, and draining fistula total count at each visit**
- **Proportion of subjects achieving HiSCR50 at visits other than Week 16**

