# 7. STATISTICAL ANALYSIS

## 7.1 Data Handling Rules and Definitions, Including Handling of Missing Data

Except where specified, all continuous variables will be summarized with descriptive statistics (the number of non-missing values, mean, standard deviation, first and third quartiles, median, minimum, and maximum). Where data have been logarithmically transformed for analysis, the summary statistics on the back-transformed data will include the geometric mean (calculated as  $\exp(m)$ ), where  $m$  is the mean of the data on the log scale) and the coefficient of variation (calculated as  $100\sqrt{[\exp(s^2)-1]}$ , where  $s$  is the standard deviation of the data on the log scale). All categorical variables will be summarized with frequency counts and percentages. Tabulations will be provided based on all subjects combined, as well as separately by treatment group.

Missing data will be maintained as missing in the analysis datasets, unless specified otherwise. For variables where missing data are imputed, the analysis dataset will contain a new variable with the imputed value and the original variable value will be maintained as missing.

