#### 7.5.1 Primary Efficacy Estimand

The primary estimand, comprising five components, is as follows:

- a) The target population is subjects in the United States and Europe diagnosed for at least 6 months with HS, having lesions at Hurley Stage II or III.
- b) The primary variable is the change from baseline in AN count of an individual subject at Week 16.
- c) To handle intercurrent events such as use of rescue medications, a hypothetical strategy for estimand (**ICH E9, 2019**) will be used such that data collected following receipt of rescue medication (if any) will be considered missing in the analysis. Missing values will be imputed as described in **Section 7.5.4**. The hypothetical scenario envisaged under this estimand is what value the primary variable would have taken if the subject had not taken rescue treatment.

- d) The population-level summary measure for the primary endpoint is mean change from baseline in AN count at Week 16. The estimator for between-group comparison of the primary endpoint will be the difference in the primary endpoint between imidolimab and placebo at Week 16.
- e) The treatment conditions of interest, two imidolimab treatment regimens and one placebo regimen:
  1. Imsidolimab 400 mg injection on Day 1, followed by 200 mg on Days 29, 57, and 85;
  2. Imsidolimab 200 mg injection on Day 1, followed by 100 mg on Day 29, 57, and 85;
  3. Placebo on Days 1, 29, 57, and 85

A linear mixed model will be used for the repeated measures (MMRM) with treatment, visit, treatment by visit interaction, and Hurley Stage at baseline as a categorical covariate and baseline AN count as a continuous covariate. An unstructured correlation (UN) matrix will be used to model correlation within a patient; if convergence is an issue, a Toeplitz structure may be considered. If convergence issue persists, elimination of post-baseline visits other than Week 16 may be considered. Subjects with missing data at Week 16 due to early discontinuation will be included in the model.

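### As written, the protocol classifies a dropped-out or rescued subject as flare-free; the SAP uses a different, undeclared denominator and does not say how rescue affects flare.

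*Protocol*

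**What the plan says.** Four protocol provisions meet on this endpoint.

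- Section 9.4.6.1, written for the secondary categorical endpoints: "Subjects with missing scores at a given visit will be considered to have not met the criteria of interest (ie, nonresponse".
- Section 9.4.7 lists "Percentage of subjects experiencing flare, defined as a" rise in AN count of at least 25% together with an absolute rise of at least 2, at each visit.
- The same section states "Methods for analyzing the above categorical and continuous efficacy endpoints will mirror the methods described in" Sections 9.4.6.1 and 9.4.6.2, on the ITT set. It makes no exception for unfavourable events.
- Section 9.4.4 on rescue: "the efficacy data on and after the use rescue medication will be set to missing in the efficacy analysis".

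The SAP handles flare differently. In Section 6.2.4 the denominator is the number "of subjects in treatment group with flare assessed at Week" x. Section 7.1 gives the default: "Missing data will be maintained as missing in the analysis datasets, unless specified otherwise". On rescue, Section 7.5.1 says that "data collected following receipt of rescue medication (if any) will be considered missing in the analysis", but this stands inside the primary estimand. No SAP text says whether it extends to flare. Section 8, which lists changes from the protocol, mentions neither the flare denominator nor the missing-data rule.

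**The concern.** Treating a missing score as criterion not met is conservative when the criterion is a good outcome such as HiSCR50. Flare is a bad outcome, so not meeting its criterion is the favourable result, and the same rule becomes anti-conservative.

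Missingness here may also be related to worsening. Rescue is offered for an intolerably painful lesion (Protocol 6.6). A subject needing more than two interventions in a double-blind phase must leave the study (6.6), and disease progression is a listed reason for discontinuation (7.2).

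What is at stake is how the flare table reads. An arm can look better on flare because more of its subjects have no usable AN count. The protocol and SAP also give different rates from the same data, with nothing to say which is intended.

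**Working it through.** **Planning figures.** Protocol 9.2 gives 120 subjects randomized 1:1:1, so 40 per arm. The planned 10% discontinuation before Week 16 leaves 40 x 0.90 = 36 per arm, or 108 in all, as the protocol states. That is 4 missing per arm at Week 16. Neither document gives a flare rate or a rescue rate, so every flare rate below, and every missing count other than 4, is an assumption.

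**Formulas.** At one visit in one arm, let N be the number randomized, m the number with flare missing, f the flares among the N - m assessed, and u the missing subjects who would have met the flare definition (0 <= u <= m).

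- Rate with complete data: (f + u)/N
- Protocol rule: f/N. It falls short by u/N, which is never negative.
- SAP rule: f/(N - m). It is too low only when u/m exceeds f/(N - m), that is, when missing subjects flare more often than assessed ones.
- Missing counted as flare: (f + m)/N, the upper bound.

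**One arm at the planned 10% missing (N = 40, m = 4; f is an expected count).**

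| Assumed flare rate among assessed | f | Protocol f/40 | SAP f/36 | Missing as flare (f + 4)/40 |
|---|---|---|---|---|
| 10% | 3.6 | 9.0% | 10.0% | 19.0% |
| 20% | 7.2 | 18.0% | 20.0% | 28.0% |
| 30% | 10.8 | 27.0% | 30.0% | 37.0% |
| 40% | 14.4 | 36.0% | 40.0% | 46.0% |

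The protocol rate is 1 to 4 points below the SAP rate and 10 points (4/40) below the upper bound.

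**Unequal missingness.** Assume 20% flare among assessed subjects in both arms, with 8 placebo and 4 imsidolimab subjects missing.

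- Protocol: imsidolimab 7.2/40 = 18.0%, placebo 6.4/40 = 16.0%; difference +2.0 points.
- SAP: 7.2/36 = 20.0% and 6.4/32 = 20.0%; difference 0.0.
- Missing as flare: 11.2/40 = 28.0% and 14.4/40 = 36.0%; difference -8.0 points.

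With 12 versus 4 missing, the differences are +4.0, 0.0 and -16.0 points. The sign depends on the rule, and the protocol rule favours the arm with more missing data.

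**Example in which every missing subject is flaring.** Assume 8 of 40 placebo subjects flare, 4 of them rescued; 4 of 40 imsidolimab subjects flare, 1 of them rescued; and no other missing data.

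- All flares counted: 8/40 = 20% v 4/40 = 10%, a gap of 10 points.
- Protocol: 4/40 = 10% v 3/40 = 7.5%, a gap of 2.5 points.
- SAP, if rescue makes flare missing: 4/36 = 11.1% v 3/39 = 7.7%, a gap of 3.4 points.
- SAP, if post-rescue counts are used and still show the flare: 20% v 10%, a gap of 10 points.

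The last two lines differ only through the point on which the SAP is silent.

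**Existing sensitivity analyses.** The rescue-as-failure analysis in SAP 7.5.2.2 covers HiSCR50 only. The multiple imputation and tipping-point analyses in SAP 7.5.4 are set out for the primary endpoint. None covers flare.

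**The case against.** The strongest reply is that the SAP governs. Protocol 9.4.1 leaves analysis detail to the SAP and, for default categorical summaries, allows a denominator of subjects with assessments where appropriate. Under SAP 6.2.4 and 7.1 nobody is counted as flare-free for want of data. The word nonresponse in Protocol 9.4.6.1 also shows that its rule was drafted with favourable outcomes in mind. That explains the origin of the problem but does not remove it: 9.4.7 extends the method without exception, and SAP 8 does not record a departure.

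A reader might go further and infer that the SAP also understates flare in every arm and that rescued subjects vanish under either document. The documents do not support that. An available-case rate has no built-in direction, as the 0.0 differences show. The SAP states rescue-to-missing only for the primary estimand. Protocol 6.6 requires evaluations before any intervention and has sites keep counting a treated lesion as permanently present, so post-rescue AN counts may remain usable.

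A reader might also conclude that every rescue should count as a flare in the main analysis. That is debatable, since one intolerably painful lesion need not raise the AN count by 25% and by 2.

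It is also fair that worsening is visible elsewhere. Rescue use is an endpoint of its own and discontinuation reasons are tabulated. SAP 7.5.3 names flare only for frequencies and percentages. This limits the consequence but does not correct the flare table.

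**Conclusion.** The concern holds for the protocol rule. On its literal text a dropped-out or rescued subject is flare-free at each affected visit, the rate can only equal or understate the true one, and the arm with more missing data gains. Visits assessed before dropout or rescue are untouched, and with no missing data there is no error.

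For the SAP the finding is narrower: an undeclared change of denominator, and silence on whether rescue makes flare missing. Bias in the SAP rate is conditional on missing subjects flaring more often than assessed ones, which the documents cannot show.

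At the planned 10% missing, the choice between the two documents' rules moves an arm's rate by 1 to 4 points for assumed flare rates of 10% to 40%. The larger contrasts depend on assumed unequal missingness or on counting every missing subject as a flare. Flare is exploratory; the primary and secondary results, sample size and alpha are unaffected.

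**What to change.** In SAP 6.2.4 and 7.5.3:

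- State that missing-as-not-met applies to favourable endpoints only.
- Name one flare denominator.
- State whether post-rescue AN counts, with treated lesions counted as present under Protocol 6.6, are used for flare.
- Add a sensitivity analysis on the ITT denominator that counts missing flare, including rescue-related missing, as flare. Show the number missing by arm and visit. Keep rescue-as-flare in this sensitivity analysis and out of the main definition.

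In SAP 8, declare the departure from Protocol 9.4.6.1 and 9.4.7.

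The cost is SAP wording, one extra derivation and one table, with no new data collection. The flare rate in the sensitivity analysis will look less favourable.
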